8. STUDY ENDPOINTS

Primary Endpoint(s)

- Urinary ITC levels will be measured using HPLC-based cyclocondensation assay^{14, 51}, which measures ITCs and metabolites as low as a few picomoles and has been routinely performed in [name] laboratory. The results will be adjusted by urinary creatinine level using creatinine assay kits (Caymen, Ann Arbor, MI). Cruciferae intake will be assessed using a questionnaire adapted from Thomson et al.⁵² to capture both intake and cooking styles.

Secondary Endpoint(s)

- Gene expression will be evaluated via RNA-seq as a surrogate for intermediate efficacy, conducted at Roswell Park's Genomics Shared Resource using NextSeq500 platform (Illumina Inc.). We have worked with the Genomics core to optimize the extraction of RNA samples from urine. With the addition of TRIzol™ right before the storage of the cell pellet samples, we were able to extract sufficient amounts of RNA and generate high quality RNA-seq data. Dietary intake will be evaluated by three non-consecutive 24-hour dietary recalls (two weekdays, one weekday) conducted by trained staff using the interview-administered Nutrition Data System for Research (NDSR)⁵³.
- Additional urinary metabolites and potential biomarkers will be explored using proteomic and/or metabolomic approaches.

Exploratory Endpoint(s)

- Our exploratory endpoint will be identification of barriers, facilitators, and other process-related measures relevant to informing the implementation of an evidence-based cruciferae intervention within clinical practice.

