Participant Data and Sample Collection Procedures. Research staff will contact patients who have agreed to be contacted by phone, whereby they will provide a general study overview and conduct a screening interview to confirm eligibility. The consent form will be mailed out to patients prior to the consenting discussion. We will ask the patient to mail back the consent form with the appropriate signatures. We will also provide an additional copy of the consent form for their records. We will include a paid postage pre-addressed envelope for the patient to mail back the signed consent form to study staff. Baseline Data Collection will be conducted within four weeks prior to intervention start. The Data Collector, masked to treatment assignment, will conduct telephone surveys with participants and directly enter participants' responses into pre-programmed data collection forms in REDCap^{49, 50}. Surveys will cover sociodemographic variables, faith and spirituality beliefs, dietary, and cruciferae intake (Appendix F). Additionally, 24-hour dietary recalls will be conducted and instructions (Appendix M) and a reference guide (Appendix N) will be mailed out to participants prior to their scheduled recall interview. Participants will also be mailed out track books to help keep track of their fruit and/or vegetable intake during the intervention (Appendix R). Follow-up Assessment (Appendix G1) will be conducted at 6 months following the same protocol as the baseline assessment (Appendix F). Participants will receive \$100 for completing the baseline and 6-month follow-up assessments. In addition, we will ask participants' feedback on the intervention (Appendix G2) as part of the Follow-Up Assessment (Appendix G1). The feedback questions (Appendix G2) will be given to those in the cruciferous arm only. For cruciferous arm study participants that have completed the 6-month follow-up assessment as of the March 21, 2022 Protocol revision, the study participants will be called back to complete the feedback questions (Appendix G2). These study participants will first be sent an information sheet (Appendix W) regarding the additional feedback questions before being called. When they are called regarding the study feedback questions, they will provide verbal consent before proceeding with answering the feedback questions.

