5. What percentage of your gross annual income do you give to your religious institution or to other religious causes each year?

[figure not shown]
6. On average, how much time each day (in 24 hrs) do you spend listening to religious music or radio, or watching religious TV?

[figure not shown]
7. On average, how much time each day do you spend reading religious scriptures, books, or other religious literature?

[figure not shown]
8. On average, how much time each day do you spend in private prayer or meditation?

9. On average, how much time each day do you spend as a volunteer in your religious community or to help others for religious reasons?

10. To what extent (on a 1 to 10 scale) have you decided to conform your life to the teachings of your religious faith?

We're going to finish the survey by asking your opinion about the dietary program you got.

I'm going to read some statements about the dietary program you got. Please let me know whether you completely disagree with the statement, disagree with the statement, neither agree nor disagree with the statement, agree with the statement, or completely agree with the statement.

	Completely disagree	Disagree	Neither agree nor disagree	Agree	Completely agree
1. The diet program I received met my approval.	①	②	③	④	⑤
2. The diet program I received was appealing to me.	①	②	③	④	⑤
3. I liked the diet program I received.	①	②	③	④	⑤
4. I welcomed the diet program I received.	①	②	③	④	⑤

	Completely disagree	Disagree	Neither agree nor disagree	Agree	Completely agree
1. The diet program I received fit into my lifestyle.	①	②	③	④	⑤
2. The diet program I received was suitable to my lifestyle.	①	②	③	④	⑤
3. The diet program I received was applicable to my lifestyle.	①	②	③	④	⑤
4. The diet program I received was a good match with my lifestyle.	①	②	③	④	⑤

Feasibility of Intervention Measure (FIM)

	Completely disagree	Disagree	Neither agree nor disagree	Agree	Completely agree
1. The diet program I received was implementable in my life.	①	②	③	④	⑤
2. The diet program I received was possible to do in my life.	①	②	③	④	⑤
3. The diet program I received was doable.	①	②	③	④	⑤
4. The diet program I received was easy to use.	①	②	③	④	⑤

If you are a part of Group A, there are a few feedback questions we would like to ask you at this time, is this okay?

If you are a part of Group B, you have finished the survey! Thank you so much for your time. Do you have any questions? Again, thank you for your participation in POW-R Health!

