Appendix G2. POW-R Participant Additional Questions to Follow-Up Questionnaire

These questions will be given to those in the cruciferous arm only.

Thank you so much for being a part of the POW-R study. The program you went through consisted of a mailed magazine, a phone call with one of our Roswell staff, and then 11 automated phone calls. We would like to ask the feedback questions regarding the study at this time.

1. What did you think about the magazine?

- a. What did you like about it?
- b. What would you change?

2. What did you think about the phone call with the Roswell staff person?

- a. What did you like about it?
- b. What would you change?

3. What did you think of the 11 automated calls?

- a. What did you like about it?
- b. What would you change?

4. What do you think having this program as a phone app?

You have finished the survey! Thank you so much for your time. Do you have any questions? Again, thank you for your participation in POW-R Health!

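### The 6-month survey script reveals the arm to a caller described as masked; the 24-hour recalls are exposed if they come after it and the same person does them

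*Combined protocol and SAP*

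**What the plan says.** Section 11 (Participant Data and Sample Collection Procedures) makes the masking claim: "The Data Collector, masked to treatment assignment, will conduct telephone surveys with participants". Responses go straight into "pre-programmed data collection forms in REDCap". The follow-up "will be conducted at 6 months following the same protocol as the baseline assessment". The same paragraph makes the Appendix G2 feedback part of the Appendix G1 follow-up assessment and limits it to the cruciferous arm. Appendix G2 repeats the limit at its head: "These questions will be given to those in the cruciferous arm only".

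The end of Appendix G1 puts this into the script. After the last rating item the caller says "If you are a part of Group A, there are a few feedback questions we would like to ask you at this time", while Group B is told that the survey is over.

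On the recalls, Section 11 adds "Additionally, 24-hour dietary recalls will be conducted" without naming the caller. Section 8 lists them among the secondary endpoints, "conducted by trained staff using the interview-administered Nutrition Data System for Research". Section 26 assigns collection of all project data to the data collector, a role it keeps apart from the recruiter and the interventionist. Appendix M places the final three recalls on separate days at the end of the study.

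**The concern.** A caller who must decide whether to continue to G2 learns which arm the participant is in. Section 11 describes that caller as masked, and no passage in the available text gives G2 to someone else or explains how masking is kept. The masking statement is therefore not true to the end of the 6-month survey call.

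This matters only for measurements taken after the branch by someone who has passed through it. The 24-hour recalls are the candidate. They are led by an interviewer who asks for every food, its amount and its preparation, so a caller who knows the arm could probe differently for cruciferous vegetables. If that happened, the recall-based comparison between arms would not be a masked assessment, although the plan's wording would allow it to be reported as one.

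**Working it through.** No arithmetic in the plan bears on this point, so the check sets the passages side by side.

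**Step 1. Does the masked role extend to the 6-month call?** Section 11 ties masking to the telephone surveys and says that follow-up repeats the baseline procedure. The masked data collector is therefore the expected G1 caller.

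**Step 2. Does that caller learn the arm?** G2 is part of the same assessment, is restricted to one arm, and is introduced in the G1 script by a group label. Whichever way the participant answers, the caller can tell the arms apart by the end of the call. The call-back route in Sections 11 and 30 covers only cruciferous-arm participants who had finished follow-up by the 21 March 2022 revision. Later participants meet the in-call branch.

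**Step 3. What is already recorded when the branch is reached?** In Appendix G1 the cruciferae frequency table, the condiment table and the belief scale all come earlier. So do the three program-rating blocks: 3 blocks × 4 items = 12 items. Urinary ITC and RNA-seq are laboratory measures on samples labelled with study IDs only (Sections 8, 11 and 18). Primary measurements affected by the branch itself: 0.

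**Step 4. Are the recalls exposed?** Two questions decide this.

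| Question | What points towards exposure | What is missing |
|---|---|---|
| Do the 6-month recalls follow the survey? | At baseline the survey comes first: Section 30 allows it to start at the initial call, Appendix E lists it before the three recall calls and offers it at once, and the Appendix O mailing says the recalls begin about a week later. Section 11 carries the baseline procedure to 6 months. | No passage states the 6-month order. Appendix G1 puts the survey after the study ends, and Appendix M puts the recalls at its end. |
| Does the same person do both? | Section 26 gives all data collection to the data collector. | Section 8 says only trained staff. No passage says whether the recall interviewer is masked or is the G1 caller. |

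**Step 5. Bounds.** There are three recalls per participant at 6 months (Section 8, Appendix M). If they all come before the G1 branch, or a different masked person does them, 0 are exposed. Otherwise up to 3 per participant are exposed. This applies in both arms, because the branch identifies Group B as well as Group A. The documents do not say how many participants were still to be followed up under the current script, and they give nothing from which the size of a bias could be calculated.

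**The case against.** The strongest reply is that the branch harms nothing with a specific planned analysis. It comes after the last survey item, the primary measures are safe, and Section 1 names only gene expression as the secondary outcome. Section 19 has no dedicated recall analysis; only its general wording on comparing endpoints and outcome variables could cover the recalls. All of this stands and keeps the point minor. It does not remove it, because Section 8 lists the recalls as an endpoint.

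A second reply is that masking of a behavioral trial by telephone is fragile anyway. Participants know which magazine and track book they received, and the rating items ask about their program. That is true, but a chance disclosure differs from a scripted one. The rating items are worded alike for both arms, and the branch is the one step in G1 that openly sorts participants.

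Third, Appendix W and the consent forms were not in the text available for this check. A hand-off of G2 to another caller, or a definition of Groups A and B, could be there. This limits the claim to what Section 11 and Appendices G1 and G2 say.

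A reader might also infer three stronger things, which the documents do not support:

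- **The caller looks up the group before dialling, so the cruciferae questionnaire is collected unmasked.** No passage gives the caller a group list, and the line is addressed to the participant.
- **The plan is silent on who does the recalls and when.** It gives a role (trained staff; the data collector) and a rough time (the end of the study). What it leaves open is narrower, as set out in the table.
- **Sections 8 and 26 conflict.** A data collector can be one of the trained staff, so there is nothing to reconcile.

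**Conclusion.** The point holds in a limited form and is minor. The masking statement in Section 11 and the group branch in Appendix G1 cannot both hold to the end of the 6-month call. No primary measurement is touched by the branch. Exposure of the recalls, at 0 to 3 per participant, is plausible from the baseline order and from Section 26, but it is not established.

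This rests on two readings. Group A is taken to be the cruciferous arm, which follows from the restriction on G2 but is not defined in the available text. The G1 caller is taken to be the masked data collector, because Section 11 names no one else. It would be wrong to conclude that the recalls were in fact collected unmasked or that any result is biased.

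**What to change.** Add one sentence to Section 11: at 6 months, masked staff complete all three 24-hour recalls before the G1 call reaches any arm-specific question. Then set the survey form, which is already programmed in REDCap, to show the group only after the last rating item has been entered. The cost is a small scheduling constraint and a form setting, with no extra call.

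Alternatively, remove the Group A and Group B lines from G1, end the survey identically in both arms, and ask G2 once all of that participant's 6-month outcome data are in. The call-back route in Sections 11 and 30 already provides for this. It costs one short extra call per remaining cruciferous-arm participant, at most 40 (the planned size of that arm), and some G2 answers may be lost. The caller should preferably not be the interventionist, because G2 asks for opinions of the staff phone call.

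The first option is enough. With either one, masked assessment can be reported accurately for the interviewer-collected outcomes, provided that Section 11 also states that the recall interviewer is masked.

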Appendix G2. POW-R Participant Additional Questions to Follow-Up Questionnaire

These questions will be given to those in the cruciferous arm only.

Thank you so much for being a part of the POW-R study. The program you went through consisted of a mailed magazine, a phone call with one of our Roswell staff, and then 11 automated phone calls. We would like to ask the feedback questions regarding the study at this time.

1. What did you think about the magazine?

- a. What did you like about it?
- b. What would you change?

2. What did you think about the phone call with the Roswell staff person?

- a. What did you like about it?
- b. What would you change?

3. What did you think of the 11 automated calls?

- a. What did you like about it?
- b. What would you change?

4. What do you think having this program as a phone app?

You have finished the survey! Thank you so much for your time. Do you have any questions? Again, thank you for your participation in POW-R Health!

Appendix H New York State Cancer Registry Contact Materials and Procedures

POW-R Health: Power to Redefine your Health Program NYS Cancer Registry Patient Contact and Data Handling Procedures

The procedures described in this document are standard procedures the New York State Cancer Registry (NYSCR) follows for patient contact studies.

I. Approval Process

1. Roswell Park Cancer Institute IRB approval
2. NY State Health Department Administrative approval

II. NYSCR Patient Consenting Process (i.e., physician notification and patient consent to release name, contact information, and diagnostic information to Roswell Park Cancer Institute)

Using ICD-O-3 codes provided in the study protocol, the NYSCR will conduct a search of its database to identify eligible patients who were diagnosed with stage Tis, Ta, or T1 bladder cancer in 2018 or later, who resided in one of eight counties of interest at diagnosis (Niagara, Orleans, Genesee, Erie, Wyoming, Chautauqua, Cattaraugus, and Allegany), who are 18 years of age or older, who did not receive a cystectomy, who did not have a prior cancer diagnosis within 12 months of their bladder cancer diagnosis, who did not have a subsequent more advanced bladder cancer diagnosis, and who have not died or opted out of research studies. This search will be repeated if needed until the recruitment goal is reached. The NYSCR will contact reporting facilities to obtain the patients' physician information, if missing in the database.

The NYSCR will send a letter to the physician of record for selected cases notifying him/her that the patient was identified for the study, requesting that the NYSCR be notified if the patient is deceased, too ill or otherwise unable or ineligible to participate in the study, and requesting information about the case's primary care physician if different from the contacted physician. The physician will have three weeks to respond.

If no contraindication is received from the physician or if the physician has not responded within three weeks, the NYSCR will send an informational packet to the patient. The packet will contain: 1) a letter explaining the study and requesting permission to release their name, contact information, and diagnostic information to the study's principal investigator at Roswell Park Cancer Institute; 2) a participant information sheet; and 3) a release of information consent form. If the NYSCR has not received any response after two weeks a reminder packet of information will be sent. Again, if no response is forthcoming after two more weeks, five telephone calls will be attempted by the NYSCR (three during regular business hours, and two during non-business hours) to describe the study and receive a response (either consent or refusal). If the patient consents verbally, NYSCR staff will fill out the consent form and document that the consent was obtained via phone. If the Registry is unable to contact the patient via telephone, and no written response has been received, no other contact will be attempted, and the patient will be considered a refusal.

Upon receipt of the consent form, the patient's name, contact information, and diagnostic information will be provided by the NYSCR to the study's principal investigator at Roswell Park Cancer Institute via Roswell's secure File Transfer Solution (sFTP). The NYSCR will receive a unique user name and password in separate emails to transfer the data via sFTP.

III. Roswell Park Patient Contact Procedures

Upon receipt of the patient information from the NYSCR, the Roswell Park research team will contact the patient by telephone. All members of the Roswell Park research team will have completed Collaborative Institutional Training Initiative (CITI training). If the patient is not reached during the first attempt, the research team will make additional attempts using the following algorithm: five additional attempts at varying dates and times, for a total of six attempts over three weeks. Each attempt will be documented in the call manager portion of the Electronic Data Capture system. After all phone attempts are exhausted, a traceable Hard to Reach Letter will be mailed to the patient's address listed in the patient profile. The patient will be asked to contact the Roswell Park research team if they are interested in learning more about the study.

Upon contact with the patient, the Roswell Park research team member will again explain the study, administer the screening interview, and obtain consent for the patient's participation. The Roswell Park research team will record the patient's real time responses in the corresponding Patient Phone Screening Interview Form in the Electronic Data Capture system. The patient will be mailed a consent form for them to keep. For respondents who do not wish to participate, the telephone contact will be terminated, and they will be ineligible for the study. Information on non-participants will be provided to the NYSCR, as well as any information for any individuals who indicate that they do not want to be contacted about any future research studies.

IV. Data Handling, Dissemination and Storage Procedures

After receipt of the patient information from the NYSCR, the data will be entered and stored in REDCap. REDCap is a secure application supported by Partners Research Computing, Enterprise Research Infrastructure & Services (ERIS). ERIS has all the necessary physical and operational securities in place to meet or exceed Federal and State security and privacy regulations for data transmission and storage using REDCap. The dataset containing patient contact information will be separated from the research dataset including survey data and urine sample tracking data. The data will only be accessed by key members of the Roswell Park research team who are in charge of contacting patients. All the data communications between NYSCR and Roswell Park will be transferred via Roswell's secure File Transfer Solution (sFTP). A unique username and password will be used for each data transfer and sent in separate emails.

Exhibit A

The following information will be provided to Roswell Park for each bladder cancer case identified for possible inclusion in the study:

1. Reporting source
2. Patient name
3. Patient address and telephone number
4. Physician name and contact information
5. Basic demographic information (race, ethnicity, date of birth, county of residence)
6. Primary site
7. Summary stage
8. Histology
9. Laterality
10. Date of diagnosis
11. Age at diagnosis
12. First course of treatment
13. Primary surgical procedure
14. Chemotherapy
15. Date of last contact

Materials used by the New York State Cancer Registry for the

POW-R Health: Power to Redefine your Health Program
[Letter from NYS Cancer Registry to Physician]

Month, Day, Year

{Physician Name}
{Physician Address}
{Physician City, State Zip}

Dear Dr. "M.D._LAST NAME":

We are writing to inform you that the New York State Department of Health's Cancer Registry is collaborating with Roswell Park Comprehensive Cancer Center on a pilot study of a dietary intervention with a goal to reduce the risk of recurrence in individuals diagnosed with non-muscle invasive bladder cancer. Patients diagnosed with non-muscle invasive bladder cancer (including Tis, Ta, and T1 disease) who did not receive cystectomy and who live in the counties of Niagara, Orleans, Genesee, Erie, Wyoming, Chautauqua, Cattaraugus, and Allegany may be eligible for the study.

Our records show that one of your patients was recently diagnosed with bladder cancer and meets the study criteria. The patient's name and other identifying information reported to the Cancer Registry are on the enclosed form. We would like to contact your patient to assess their interest in participating in the study.

Patients will be sent an introductory letter describing the study and requesting their consent for their name, contact information, and some information about their diagnosis to be shared with Roswell Park Comprehensive Cancer Center. Patients who consent will be contacted by phone regarding participation in the study. Patient participation in the study includes participation in a 6-month phone-based dietary intervention that will consist of educational materials mailed to the patient's home, one 20-minute phone call with Roswell Park staff to go over the educational materials, and 11 automated telephone calls asking participants to report the number of vegetable servings they have consumed in the prior week, followed by tailored feedback based on the servings reported. Patients will also be asked to complete two assessments, one at the beginning of the study, and one at the end. These assessments will include a 45-60-minute phone survey, self-collection of a urine sample, and three 24-hour dietary recalls. All information that could identify the patient will be kept confidential. Names and other identifying information will not be used in any publication about the study.

If you do not object to our contacting your patient, you do not need to do anything further. However, there may be some reason why your patient cannot or should not be contacted about

participation in this study; therefore, we would like to hear from you within the next three weeks if you prefer that we do not contact your patient.

If you prefer that we do not contact your patient please complete the enclosed form and fax it to "Attn: bladder cancer study" at [contact] or mail it back to us in the enclosed self-addressed, stamped envelope. If you have any questions about the study or the form, please contact [name] at the New York State Cancer Registry at [contact]. Thank you very much for your assistance.

Sincerely,

[name].
Director, New York State Cancer Registry

New York State Cancer Registry
POW-R Health: Power to Redefine your Health Program

Patient Information Sheet for Physician

Name of Physician

Address

Address

Address

Telephone number

If information below is incorrect please provide correct information.

Patient Name

Patient Address

Telephone number

Patient DOB _____ Sex _____

Race _____

Diagnosed with non-muscle invasive Tis, Ta, or T1 bladder cancer?

Yes _____ No _____

If yes, date first diagnosed _____

Any medical contraindications to patient contact for the study? Yes _____ No _____

If yes, please explain _____

Physician signature _____ Date _____

Please fax the completed form to "Attn: bladder cancer study" at [contact]. Or mail the form in the enclosed self-addressed, stamped envelope to:

POW-R Health: Power to Redefine your Health Program, New York State Cancer Registry,
NYS Department of Health, [name]

Thank you for your assistance.

Date sent

[Letter from NYS Cancer Registry to Patient]

{Patient Name}

{Patient Street Address}

{Patient City, State, ZIP}

Dear _____:

The New York State Department of Health's Cancer Registry is contacting patients who may be eligible for a research study. The study is being done in collaboration with researchers at Roswell Park Cancer Institute. The purpose of the study is to learn more about how diet may reduce the risk of recurrence in individuals with early-stage bladder cancer. Men and women who were recently diagnosed with early-stage bladder cancer and who live in the counties of Niagara, Orleans, Genesee, Erie, Wyoming, Chautauqua, Cattaraugus, and Allegany may be eligible for the study.

Under New York State Public Health Law, hospitals and doctors must report all cases of cancer that they find to the New York State Cancer Registry. This is how we learned about your diagnosis.

